### 6.1.2 DOSING AND ADMINISTRATION

In regard to drug administration, participants will be required to take Epidiolex with food. Of note, symptoms of food selectivity and food refusal are seen frequently in ASD (65). Therefore, if caregivers report that their child has initial difficulties accepting the CBD, the study clinicians will work on increasing participant tolerance and acceptance of the CBD through the use of standard behavioral intervention strategies for up to one week. If the participant continues to reject the dose he/she was assigned after one week of trial initiation, he/she will be withdrawn from the study.

Related to dosing, in Part 1 of the study, we employed the BOIN design (66, 67) in the first five cohorts of this open trial to estimate the optimal dose. The BOIN design was selected because it is more flexible than the traditional 3+3 design and possesses superior operating characteristics that are comparable to those of the more complex model-based designs, such as the continual reassessment method (CRM) (68).

We defined a target response rate for the optimal dose is  $\phi = 0.60$  and a maximum sample size of 30. We enrolled and treated participants in cohorts of size 3. The trial design was implemented through the following three steps:

1. Participants in the first cohort were treated at Dose Level 2 (see Table 1).
2. To assign a dose to the next cohort of participants, we conducted dose escalation/de-escalation according to the rule displayed in Table 2, which minimizes the probability of incorrect dose assignment with response rates of  $\phi_1 = 0.684$  and  $\phi_2 = 0.52$  designated as the uncertainty interval. When using Table 2, please note the following:
  - a. "Eliminate" means that we eliminate the current dose from the trial to prevent treating any future participants at this dose because the response rate is too low.
  - b. When we eliminate a dose, automatically de-escalate the dose to the next lower level.
  - c. If none of the actions (i.e., escalation, de-escalation or elimination) is triggered, we treat the new participants at the current dose.
  - d. If the current dose is the lowest dose and the rule indicates dose de-escalation, treat the new participants at the lowest dose.
  - e. If the current dose is the highest dose and the rule indicates dose escalation, treat the new participants at the highest dose.
3. Repeat step 2 until the maximum sample size of 30 is reached.

**Table 1.** Dose levels

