Dose Level 1	Dose Level 2	Dose Level 3
3 mg/kg/day	6 mg/kg/day	9 mg/kg/day

**Table 2.** Dose escalation/de-escalation/elimination rules for the BOIN Design and results in the first 5 cohorts

Cohort	1	2	3	4	5	6	7	8	9	10
Number of participants treated at the current dose	3	6	9	12	15	18	21	24	27	30
Dose administered (mg/kg/d)	6	6	3	3	6	-	-	-	-	-
Cumulative N of respondents	1	3	4	4	5	-	-	-	-	-
Escalate if # of responses >=	3	5	7	9	11	13	15	17	19	21
Deescalate if # of responses <=	NA	3	4	6	7	9	10	12	14	15
Eliminate if # of responses <=	NA	1	2	4	5	7	8	10	12	13

For purposes of the study design, participants were categorized as either “responders” or “non-responders” at the end of the 6-week intervention phase in order to determine the dose level for the following cohort. This categorization was based upon the following procedures.

- After completing and meeting eligibility criteria, study staff (including child psychologists and psychiatrists with expertise in ASD and comorbid symptoms) met to consensus on an individualized, primary outcome variable for each participant at the enrollment/baseline visit. The primary target was what is most interfering in the child’s functioning at the time of assessment and chosen based upon informant report, scores from a battery of standardized assessments covering a wide range of core and associated symptom

- domains, and clinical observations. Clinician consensus also yielded a Clinical Global Impression-Severity (CGI-S) score to represent the study team's impression of the participant's current severity of illness.
- After the final study visit, study staff met again to consensus on the degree of improvement observed in the predetermined primary outcome variable for each child. A CGI-S score was also determined. Definitions of response and non-response are provided below.
    - Response: In the absence of dose limiting effects, a Clinical Global Impression Scale – Improvement (CGI-I) score of 1 (very much improved) or 2 (much improved) determined by consensus based upon clinical judgment, informant report, and change in scores on measures (using the Reliable Change Index when possible) relevant to the predetermined primary outcome.

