#### 9.4.2 ANALYSIS OF THE PRIMARY EFFICACY ENDPOINT(S)

We will select as the optimal dose the dose for which the isotonic estimate of the response rate is closest to the target response rate. If there are ties, we will select the higher dose level when the isotonic estimate is lower than the target response rate and we will select the lower dose level when the isotonic estimate is greater than or equal to the target response rate.

As mentioned, response rate will be determined by the proportion of participants classified as responders. A treatment response is defined as a CGI-I score of 1 or 2 on the individualized, predetermined primary outcome variable, whereas a nonresponse is a CGI-I score of 3 or greater. Scores on the CGI-I will be determined by clinician consensus.

Table 5 shows the operating characteristics of a 5-dose BOIN design based on 1000 simulations. The operating characteristics show that the design selects the true optimal dose, if any, with high probability and allocates more participants to the dose levels with the response rate closest to the target of 0.6. Please refer to Tables 3 and 4 for the design and statistical expectations relevant to Part 2 of the study.

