**Table 5. Operating characteristics of the BOIN design: Part 1**

	Dose 1	Dose 2	Dose 3	Dose 4	Dose 5	# of Participants	% Early Stopping
True Response Rate	0.4	0.5	0.6	0.55	0.45		
Selection %	17.1	9.3	21.8	22.0	1.7		28.1
# Participants treated	5.84	4.39	10.55	5.36	0.86	27	

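### Table 5 does not support the claim that the design finds the optimal dose with high probability, and it simulates five doses where Part 1 had three

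*Combined protocol and SAP*

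**What the plan says.** Section 9.4.2 selects as optimal the dose whose isotonic estimate of the response rate is closest to the target, which section 6.1.2 sets at 0.60. It then introduces its evidence: "Table 5 shows the operating characteristics of a 5-dose BOIN design based on 1000 simulations". From that table it draws this conclusion about the design: it "selects the true optimal dose, if any, with high probability and allocates more participants to the dose levels with the response rate closest", where closeness is measured against that target.

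The table's caption is "Operating characteristics of the BOIN design: Part 1". It gives one scenario, with true response rates 0.4, 0.5, 0.6, 0.55 and 0.45 for doses 1 to 5.

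The Part 1 design is in section 6.1.2. Table 1 lists three levels: 3, 6 and 9 mg/kg/day. On the start it says: "Participants in the first cohort were treated at Dose Level 2". Later cohorts were assigned "according to the rule displayed in Table 2", with 0.684 and 0.52 "designated as the uncertainty interval". For Part 2, section 9.4.2 refers the reader to Tables 3 and 4.

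**The concern.** The sentence states a design property for the primary endpoint and cites a table as proof. The table shows the dose at target being selected in about one run in five. The table also describes a design with a different number of doses from the one its caption names.

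This sentence and table are the plan's only numerical support that the Part 1 rule can find the optimal dose. Part 1 has already produced results (4/9 responders at 6 mg/kg/day, 1/6 at 3 mg/kg/day), and the protocol reads them as information about dose. If the phrase is carried into a report, readers will be told that a dose-finding rule with demonstrated high reliability lay behind those results. The plan contains no such demonstration.

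**Working it through.** **Inputs from Table 5**

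| | Dose 1 | Dose 2 | Dose 3 | Dose 4 | Dose 5 | Early stopping |
|---|---|---|---|---|---|---|
| True rate | 0.40 | 0.50 | 0.60 | 0.55 | 0.45 | |
| Selected, % | 17.1 | 9.3 | 21.8 | 22.0 | 1.7 | 28.1 |
| Mean treated | 5.84 | 4.39 | 10.55 | 5.36 | 0.86 | |

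**1. Is the table internally sound?** Selection plus stopping: 17.1 + 9.3 + 21.8 + 22.0 + 1.7 + 28.1 = 100.0. Participants: 5.84 + 4.39 + 10.55 + 5.36 + 0.86 = 27.00, the printed total. Neither sum suggests a misprint.

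**2. Can 21.8% be reproduced?** Approximately. A five-dose simulation in this scenario (40,000 runs) used cohorts of 3, a maximum of 30 and a start at dose 3. Elimination removed the dose and all higher doses, and selection used inverse-variance isotonic weights. With de-escalation at 1 or fewer of 3 responders, dose 3 was selected in 23.4% of runs, 28.5% stopped early and the mean sample size was 27.25. With no de-escalation at n=3, as Table 2 prints, the figures were 26.0%, 22.0% and 28.57. Table 5's starting dose and stopping rule are not stated, so these settings are assumptions. Doses 4 and 5 match less well (19.0% and 4.1% under the first rule, against 22.0% and 1.7% printed). Either way the figure is of the printed order, so 21.8% is not a slip.

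**3. Which dose is optimal in this scenario?** Dose 3. It is the only dose at 0.60 and also has the highest rate, so the endpoint definition in section 3 and the selection rule in section 9.4.2 agree. Because a dose at target exists, early stopping here is a miss.

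**4. How often is it found?**
- Of all runs: 21.8%. Simulation standard error: sqrt(0.218 × 0.782 / 1000) = 1.3 percentage points.
- Of runs that select a dose: 100 − 28.1 = 71.9%, so 21.8 / 71.9 = 30.3%. For dose 4, 22.0 / 71.9 = 30.6%.
- Dose 3 against dose 4: the difference is 0.2 points, with standard error sqrt((0.218 + 0.220 − 0.002²) / 1000) = 2.1 points. The two cannot be told apart.

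**5. More generous readings**
- Either dose with a true rate inside 0.52 to 0.684 (doses 3 and 4): 21.8 + 22.0 = 43.8% of all runs.
- The same, among runs that select a dose: 43.8 / 71.9 = 60.9%.
- The remainder: a dose outside the interval, 17.1 + 9.3 + 1.7 = 28.1%; no dose, also 28.1%.

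**6. Does Table 5 describe Part 1?** Side by side: five doses in section 9.4.2 and Table 5; three doses starting at level 2 in section 6.1.2 and Table 1. Table 4 covers only the 9 mg/kg/day extension. No table covers the three-dose rule.

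**The case against.** The best case for the plan is that the scenario is hard: dose 4 is only 0.05 below target, so choosing it costs little. If it counts as a success and stopped runs are set aside, the figure is 60.9%. The text also discloses that five doses were simulated, all endpoints are declared exploratory (section 4.1), and Part 2 relies on Tables 3 and 4. Much of this stands, and it limits the consequence. It does not rescue the wording. The 60.9% needs both concessions at once, and setting aside stopped runs removes failures. The disclosure in the text does not correct the caption.

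Four stronger inferences are tempting, and the documents do not support them.

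- *That Part 1 had only a 21.8% chance of finding its dose.* The figure belongs to a five-dose design. It contradicts the sentence that cites it but does not measure the three-dose rule, which could do better or worse. Its performance would depend on elimination handling and isotonic weighting that the plan does not spell out, so no three-dose percentage is offered here.
- *That the allocation half of the sentence is false.* Doses 3 and 4, the two closest to target, receive (10.55 + 5.36) / 27 = 59% of participants, and dose 3 receives the most. Dose 1 does receive more than dose 4, but the sentence promises no full ranking.
- *That the NA for de-escalation at n=3 in Table 2 is an error, so cohort 2 was misdosed.* The 0.52 limit alone would give 1 or fewer (0.52 × 3 = 1.56), but section 6.1.2 makes Table 2 the operative rule and keeps the current dose when no action is triggered. Elimination is also NA at n=3, which is consistent with a deliberate minimum of six. Cohort 2 was dosed as the table directs.
- *That Table 5 and Table 2 used different rules at n=3.* The closer match in step 2 hints at this, but it rests on assumed settings.

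**Conclusion.** The point holds as a mismatch between a stated design property and the table cited for it. Table 5 shows the dose at target selected in 21.8% of runs (30.3% of runs that select a dose), no more often than a dose at 0.55 and less often than stopping early. The more lenient count of doses 3 and 4 reaches 43.8% of all runs. None of these is a high probability. Separately, the table is captioned for Part 1 but simulates a different number of doses, so the reliability of the Part 1 rule is undocumented rather than shown to be poor.

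The percentages come straight from the printed table. The one choice made is to use the 0.52 to 0.684 decision limits as a yardstick for true rates, and that favours the plan. The conclusion does not rest on the simulation in step 2. The consequence is confined to reporting: the observed 4/9 and 1/6 stand as data, but a dose conclusion drawn from them should not be described as coming from a rule shown to be reliable.

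**What to change.** In section 9.4.2, delete the words about high probability or replace them with the printed figures: 21.8% for the dose at target, 43.8% for either dose inside 0.52 to 0.684, and 28.1% stopped early. The allocation wording can stay.

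Then do one of two things with Table 5.

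- *Minimum:* recaption it as an illustrative five-dose design, and state that operating characteristics for the three-dose design were not computed.
- *Better:* replace it with a simulation of the three-dose design as run: start at level 2, cohorts of 3, maximum 30, and Table 2 as printed including NA at n=3, under at least one rising and one inverted-U scenario. State the isotonic weighting and the elimination handling used. The latter needs spelling out because section 6.1.2 describes only a move to the next lower level, and none exists below 3 mg/kg/day, where 1/6 met the elimination limit and cohort 5 was then treated at 6 mg/kg/day.

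The minimum costs a few words, and the fuller version a short simulation. Neither changes trial conduct, Part 2, or any data already collected.

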**Table 5. Operating characteristics of the BOIN design: Part 1**

	Dose 1	Dose 2	Dose 3	Dose 4	Dose 5	# of Participants	% Early Stopping
True Response Rate	0.4	0.5	0.6	0.55	0.45		
Selection %	17.1	9.3	21.8	22.0	1.7		28.1
# Participants treated	5.84	4.39	10.55	5.36	0.86	27	

#### 9.4.3 ANALYSIS OF THE SECONDARY ENDPOINT(S)

Our secondary objective is to quantify the effect size of changes in a wide range of candidate measures that may reveal response to CBD. Effect sizes and 95% confidence intervals will be reported for all measures obtained at enrollment/baseline and at the final visit (or last observation, in cases of early termination).

#### 9.4.4 SAFETY ANALYSES

Safety endpoints will be analyzed as summary statistics during treatment and as change scores from baselines. Adverse events will be coded per the Medical Dictionary for Regulatory Activities (MedDRA). Each AE will be counted once only for a given participant. Adverse events will be presented in terms of severity, frequency, and relationship of AEs to study intervention by System Organ Class (SOC) and preferred term groupings. For each AE, start date, stop date, severity, relationship, expectedness, outcome, and duration will be reported. Adverse events leading to premature discontinuation from the study intervention and serious treatment-emergent AEs will be presented either in a table. The information included here should be consistent with the information contained within **Section 8.2, Safety and Other Assessments**.

#### 9.4.5 BASELINE DESCRIPTIVE STATISTICS

The demographic characteristics and the baseline measurements of all participants will be summarized using standard descriptive statistics (e.g., means, medians, standard deviations, and ranges for continuous variables and frequencies for categorical variables).

#### 9.4.6 PLANNED INTERIM ANALYSES

After each cohort completes participation in the 6-week treatment period, classification of participants as “responders” or “non-responders” will occur based upon the definitions provided above. The subsequent cohort will be administered the dose level indicated given the response of the previous cohorts.

#### 9.4.7 SUB-GROUP ANALYSES

Not applicable.

#### 9.4.8 TABULATION OF INDIVIDUAL PARTICIPANT DATA

Individual participant data will be listed by measure and time point.

#### 9.4.9 EXPLORATORY ANALYSES

The objective of obtaining MRI data is to determine the feasibility of obtaining possible biomarkers of treatment response in children and adolescents with ASD and to conduct preliminary analyses, if sufficient data are collected. For all participants who agree to undergo MRI before and after treatment with Epidiolex, resting-state functional connectivity analyses will be conducted.

## 10 SUPPORTING DOCUMENTATION AND OPERATIONAL CONSIDERATIONS

### 10.1 REGULATORY, ETHICAL, AND STUDY OVERSIGHT CONSIDERATIONS

#### 10.1.1 INFORMED CONSENT PROCESS

##### 10.1.1.1 CONSENT/ASSENT AND OTHER INFORMATIONAL DOCUMENTS PROVIDED TO PARTICIPANTS

Consent forms describing in detail the study intervention, study procedures, and risks are given to the parents/guardians of participants and written documentation of informed consent is required prior to starting intervention/administering study intervention. The consent and assent materials are submitted with this protocol.

##### 10.1.1.2 CONSENT PROCEDURES AND DOCUMENTATION

Informed consent is a process that is initiated prior to the individual's agreeing to participate in the study and continues throughout the individual's study participation. Consent forms will be IRB-approved and the participant's parent/guardian will be asked to read and review the document. The research staff will explain the research study to the participant's parent/guardian and answer any questions that may arise. A verbal explanation will be provided in terms suited to the participant's parent/guardian comprehension of the purposes, procedures, and potential risks of the study and of their rights as research participants. Participants and their parent/guardian will have the opportunity to carefully review the written consent form and ask questions prior to signing. The participants and their parent/guardian should have the opportunity to discuss the study with their family or surrogates or think about it prior to agreeing to participate. The participant's parent/guardian will sign the informed consent document prior to any procedures being done specifically for the study. Participants and their parent/guardian must be informed that participation is voluntary and that they may withdraw from the study at any time, without prejudice. A copy of the informed consent document will be given to the participant's parent/guardian for their records. The informed consent process will be conducted and documented in the source document (including the date), and the form signed, before the participant undergoes any study-specific procedures. The rights and welfare of the participants will be protected by emphasizing to them that the quality of their medical care will not be adversely affected if they decline to participate in this study.

Importantly, while the COVID-19 pandemic still presents a risk to participants and staff, we will reduce the number of required in-person visits and instead conducting those visits virtually over WebEx. All procedures in the screening visit, with the exception of the blood draw, will be conducted virtually and will continue to be conducted virtually based on individual family preferences. Therefore, our written consent/assent processes will be conducted via WebEx, albeit in the same way it would be done in person. The parent/guardian will be provided the written consent form prior to the screening visit and

encouraged to review it. At the beginning of the virtual screening visit, while sharing the consent form on the screen, the research staff member will explain the research study to the participant's parent/guardian and answer any questions that may arise. A verbal explanation will be provided in terms suited to the participant's parent/guardian's comprehension of the purposes, procedures, and potential risks of the study and of their rights as research participants. A research staff member will also meet with the child participant on WebEx to review the age-appropriate assent form in the same way. Participants and their parent/guardian will have the opportunity to carefully review the assent and consent forms and ask questions prior to signing electronically. To adjust the consenting process for virtual administration, we will present the consent and assent forms and collect signatures through REDCap survey. Parents will be provided REDCap links to the consent and assent forms so they can follow along while the research team reviews study procedures and can then provide signatures indicating consent/assent. A copy of the signed consent form on REDCap will be provided electronically to the participant's parent/guardian for their records.

---

### 10.1.2 STUDY DISCONTINUATION AND CLOSURE

This study may be temporarily suspended or prematurely terminated if there is sufficient reasonable cause. Written notification, documenting the reason for study suspension or termination, will be provided by the suspending or terminating party to study participants, investigators, and regulatory authorities. If the study is prematurely terminated or suspended, the PI will promptly inform study participants, the IRB and will provide the reason(s) for the termination or suspension. Study participants will be contacted, as applicable, and be informed of changes to study visit schedule.

Circumstances that may warrant termination or suspension of the study include, but are not limited to:

- Determination of unexpected, significant, or unacceptable risk to participants
- Insufficient compliance to protocol requirements
- Data that are not sufficiently complete and/or evaluable
- Determination that the primary endpoint has been met
- Determination of futility

Study may resume once concerns about safety, protocol compliance, and data quality are addressed, and satisfy the IRB and/or FDA.

---

### 10.1.3 CONFIDENTIALITY AND PRIVACY

Participant confidentiality and privacy is strictly held in trust by the participating investigators and their staff. This confidentiality is extended to cover testing of biological samples and genetic tests (if any) in addition to the clinical information relating to participants. Therefore, the study protocol, documentation, data, and all other information generated will be held in strict confidence. No information concerning the study or the data will be released to any unauthorized third party without prior written approval of the IRB.

All research activities will be conducted in as private a setting as possible.

Representatives of the IRB, regulatory agencies or pharmaceutical company supplying study product may inspect all documents and records required to be maintained by the investigator, including but not limited to, medical records (office, clinic, or hospital) and pharmacy records for the participants in this study. The clinical study site will permit access to such records.

The study participant's contact information will be securely stored at each clinical site for internal use during the study. At the end of the study, all records will continue to be kept in a secure location for as long a period as dictated by the reviewing IRB or Institutional policies.

Study participant research data, which is for purposes of statistical analysis and scientific reporting, will be transmitted to and stored at the NYU Child Study Center. This will not include the participant's contact or identifying information. Rather, individual participants and their research data will be identified by a unique study identification number. The study data entry and study management systems used by clinical sites and by NYU Child Study Center research staff will be secured and password protected. At the end of the study, all study databases will be de-identified and archived at the NYU Child Study Center.

Audio/visual recordings of the BOSCC took place prior to discontinuing its administration due to the COVID-19 pandemic, as they are required to be able to score the behaviors during the interview to assess quantitatively whether social communication ability has changes. These recordings were labeled only with the participant's study identification number and will be kept in the Investigator's files. The video may show the participant's face, and if his/her name is spoken during the session, it will be recorded as part of the video. Parents were made aware of this, and consent was attained specifically for audio/visual recording. It was our intention to pursue expert analysis of these recording, if and when available, from the developer, [name], world-renown researcher and expert in autism evaluation, and her team at UCLA. This coding service as well as the coding scheme for the BOSCC are currently being established. We expect that they will become available within the next year or so while this study is still active. Because coding of videos is not absolutely necessary until the end of this trial, we are fairly confident that UCLA will have finalized this service in time to pursue expert analysis of our complete dataset. For context, seeking these services from [name] team is essential; the BOSCC is a novel measure and evaluating change in the subtle symptoms of high-functioning autism is complex. Observational measurement of change will likely be unmanageable without their support. Further, using outside coders will allow for blinding of observers who will not be informed about whether the video they are coding is the first administration from the enrollment/baseline visit or the second administration from the final visit. This blinding would not be possible if coding was completed internally. Importantly, [name] and her team would not have access to these recordings until proper IRB-approved protocols and contracts are in place at both institutions, and the investigators on the current study will provide all documentation necessary to the NYULH IRB prior to initiating the consultative relationship with UCLA. Once the coding service has been approved and ready to be implemented, we will submit a Modification to include these intentions in the audio/visual recording consent form and informed consent form, to enable participants to consent to the recordings knowing of our intention to obtain authorized expert assistance to analyze the videos at a later date. Following the onset of the COVID-19 pandemic, we discontinued administration of the BOSCC. We will not administer the BOSCC for the remainder of the trial, as the requirement for participants and staff to have effective face masks during COVID makes it impractical to perform the BOSCC.

---

